## Organization of the research:

This study is an investigator initiated study in collaboration with Infectious Diseases Department, HUH and with Obesity Research Unit, University of Helsinki.

The research project is coordinated by PI [name] and co-investigator [name].

The recruiting and clinical follow-up of study subjects will take place in Infectious Diseases Clinic, Helsinki. There will be two study visits in the Obesity Research Unit, where the metabolic procedures will be done. Additionally, liver fat and abdominal fat distribution will be measured by MRI/MRS and liver fibrosis by transient elastography, both at the Helsinki University Hospital.

Funding of this project comes from Merck Sharp & Dohme Corp. With this funding, we anticipate to organize the study visits of the study subjects in Obesity Research Unit and all the metabolic and imaging studies planned for this study. In the future, we will apply funding for stool sample analyzes (microbiome studies) and for the gene expression studies of the fat biopsies.

# 1. Background and rationale of the study

The prevalences of overweight (body-mass-index, BMI 25-30 kg/m^2) and obesity (BMI>30 kg/m^2) are steadily increasing among HIV-infected patients globally. In our HIV outpatient clinic in Helsinki, approximately half of the patients are overweight or obese (unpublished data). Obesity is often associated with metabolic syndrome, which manifests with dyslipidemia (with high triglycerides and low high-density lipoprotein cholesterol (HDL) levels), impaired fasting glucose ( $\geq 5.6$  mmol/l), high blood pressure (BP $\geq 130/\geq 85$  mmHg) and increased visceral adipose tissue mass. Inflammation markers, such as hsCRP and IL6 are often increased in serum and there are various alterations in bowel microbiota supporting ongoing low-grade inflammation. Similar changes in inflammation markers and in metabolism are seen in HIV-infected patients even with normal body weight.

As the prevalences of obesity and metabolic disorders among HIV patients gradually increase, the risk of non-alcoholic fatty liver disease (NAFLD) increases parallel, as shown by the ECHAM (European Cohort on HIV, Ageing and Metabolic liver disease) Study (1). NAFLD is characterized by excessive hepatic fat accumulation and defined by the presence of steatosis in >5% of hepatocytes according to histological analysis or by a weight fraction >5.6% assessed by proton magnetic resonance spectroscopy (1HMR) or proton density fat fraction – a quantitative chemical shift-based water and fat separation -magnetic resonance imaging (MRI), which are the golden standards in diagnostics (2). The diagnosis of NAFLD requires the exclusion of secondary causes, such as excessive daily alcohol consumption (3). NAFLD, however, is a spectrum of pathologically distinct liver diseases, where simple steatosis is considered to be a non-progressive form of NAFLD, and non-alcoholic steatohepatitis (NASH) is considered to be the progressive form of NAFLD. NASH manifests with inflammation and fibrosis and can lead to cirrhosis and hepatocellular carcinoma (HCC) (2). Clinically alarming are the data which suggest that HIV infected individuals have higher rates of progressive form of NAFLD than non-HIV infected age, gender and BMI matched controls (4).

Antiretroviral therapy (ART) for HIV-infected patients may promote unfavourable changes in metabolism and in trunk fat redistribution. Antiretroviral drugs may increase biosynthesis and reduce hepatic clearance of serum cholesterol. In a systematic review regarding ART-associated changes in metabolism, association between ART exposure and mean serum total cholesterol level and triglycerides was significantly stronger with the use of protease inhibitors (PI), compared with the use of other ART regimens (5). Yet the clinical effect of individual agents within the PI class varies. Other antiretroviral medications may contribute to dyslipidemia as well. Of the NNRTI-group (non-nucleoside reverse transcriptase inhibitor), efavirenz has been associated with the worst lipid profile, causing elevated triglycerides and total cholesterol and unfavourable body fat redistribution (5).

According to several studies, raltegravir (RAL) has been shown to have neutral metabolic effects in the management of HIV. In (ACTG) A5257 study, when treatment-naive adult subjects were randomized either to ritonavir-boosted protease inhibitor atazanavir (ATV/r) or darunavir (DRV/r), or RAL-based ART, RAL produced the most favorable lipid profile (6). In SPIRAL-trial, ART-treated, virologically suppressed HIV-infected patients switching from a PI/r containing ART to RAL-based ART showed a favourable impact on lipids (lowering of triglycerides, total and LDL cholesterol) as compared to those continuing with the PI/r based ART. (7). In the same study, insulin and some inflammatory biomarkers decreased in the RAL-arm (hsCRP, IL-6, TNF- $\alpha$ ). In a study conducted by Nguyen et al (SWITCH-ER study), favourable changes in total cholesterol, triglycerides and LDL cholesterol were seen in the RAL-arm compared to the control arm continuing their current efavirenz-containing ART (8).

Although raltegravir has been demonstrated to have beneficial impact on some metabolic parameters compared to the PI class or to efavirenz, very little is known whether raltegravir could improve hepatic steatosis in HIV-associated metabolic syndrome. Recent studies presented in CROI (Conference on Retroviruses and Opportunistic Infections) 2017 showed that serum

biomarker Chi3L1 (hepatic steatosis/fibrosis marker) decreased in HIV-infected women with lipohypertrophy when switching from NNRTI- or PI-based regimens to raltegravir. In the same study adiponectin concentration decreased, which is surprising knowing the inverse correlation between serum/plasma adiponectin concentration and liver fat content (9, 10). STERAL study presented also in CROI 2017, showed that switching from efavirenz to raltegravir decreased hepatic steatosis, as measured by controlled attenuation parameter (CAP) at 48 weeks, compared with those continuing with efavirenz in HIV/HCV co-infected patients (11).

There are confounding data on the effect of raltegravir on body weight and fat tissue. In a study with thirty-nine obese women, a switch to raltegravir from a PI or a NNRTI did not reduce visceral fat as measured by computed tomography (12). In SPIRAL-LIP substudy there were no significant changes in total body fat between maintaining a PI-based regimen or switching to a raltegravir-based regimen as measured by DEXA and CT. However, maintaining a PI-based regimen was associated with a significant increase in visceral adipose tissue and total adipose tissue (13). In a retrospective analysis of the ACTG A5257 study, where ART-naïve HIV-infected individuals were randomized to one of 3 regimens: atazanavir/ritonavir (ATV/r), darunavir/ritonavir (DRV/r), or raltegravir (RAL) each in combination with tenofovir/emtricitabine, the odds of severe weight gain were significantly higher for RAL than for ATV/r and for DRV/r (14).

In summary, raltegravir seems to have a favourable impact on distinct metabolic components compared to PI class or efavirenz. Raltegravir also seems to decrease hepatic steatosis measured by CAP in HIV-infected subjects co-infected with HCV. These intriguing results set up a hypothesis whether raltegravir could improve liver fat content in HIV-infected population without HCV, who are overweight or obese and have other metabolic syndrome components and who currently use a PI or efavirenz in their ART. To test this hypothesis, we plan to run a prospective, randomized, open, parallel design study to compare the liver fat content in study subjects either continuing their current ART regimens (which include a PI or efavirenz) or switching to raltegravir based ART. For the quantification of liver fat content, we aim to use the proton magnetic resonance spectroscopy – the golden standard method -, which has not been used previously in PI/ efavirenz/ raltegravir-switch studies.

As there are confounding data on body fat composition changes with raltegravir in studies using single slice CT scan and DEXA methods, the plan is to characterize the adipose tissue changes in more detail with MRI, using 16 slices described in more detail below in methods. To acquire more knowledge on metabolic effects in adipose tissue level, we also intend to take subcutaneous adipose tissue biopsies together with blood, saliva and feces samples. With these study methods we aim to characterize in more detail the metabolic effects of protease inhibitors, efavirenz and raltegravir in HIV-infected overweight or obese patients with the presence of at least one metabolic syndrome component.

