## 2. List of study objectives

Primary objective is:

1. Baseline to 24-week Change in Liver Fat (measured by proton magnetic resonance spectroscopy,  $\Delta \%$ )

Secondary objectives are:

1. Baseline to 24-week Change in Body Composition including subcutaneous and visceral adipose tissue volume (measured by magnetic resonance imaging), total body fat and lean tissue mass (measured by Bioelectrical Impedance Analysis)
2. Baseline to 24-week Change in Liver Stiffness measured by transient elastography (Fibroscan ®)
3. Baseline to 24-week Change in Glucose Metabolism including fasting glucose, insulin, 2-h oral glucose tolerance test
4. Baseline to 24-week Change in Lipid Profile (LDL and HDL cholesterol, Triglyceride)
5. Baseline to 24-week Change in Metabolic and Inflammatory Biomarkers (e.g. high-sensitivity C-reactive protein (hsCRP), adiponectin, etc)
6. To collect subcutaneous adipose tissue samples at baseline and 24 weeks for future gene expression studies
7. To collect stool and saliva samples at baseline and 24 weeks for future microbiome studies
8. To collect safety and tolerability data related to the switch to raltegravir
9. Determination of the fatty liver adipose allele (B-PNPLA3)
10. Determination of basal metabolic rate by indirect calorimetry at screening and at the end of study

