## 3. Study subjects

Actual subject recruitment will start after ethics committee (EC), competent authority (CA) and clinic approvals have been granted. The study subjects will be recruited and screened in a single center (Aurora hospital, Infectious diseases clinic, HUH, Helsinki). All the eligible study subject candidates will be contacted during regular visits and informed of the study by study investigators verbally and with a written information hand out. After adequate time and opportunity to inquire about details of the study and to decide whether or not to participate in the study, the candidates will sign and personally date an informed consent. After the study has finished, all the study subjects will continue their regular follow up with a chance to continue their current ART or to switch to another regimen.

The total number of study subjects included in the study is 45. Study subjects will be randomized 1:1 to continue current ART regimens or to switch their PI or efavirenz to once daily raltegravir

plus continue current NRTIs. The randomization will be stratified by age, sex and antiretroviral regimens (PI or efavirenz).

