**The inclusion criteria are:**

- Written informed consent (IC) obtained.
- HIV-positive adult (age over 18) subjects currently on stable ART, with no changes in the ART regimens during the past 6 months.
- Current ART includes either a protease inhibitor or efavirenz.
- No documented or suspected resistance to integrase inhibitors or to NRTIs.
- No prior history of virologic failure. Failure is defined as a confirmed plasma viral load  $> 200$  cop/ml measured no less than six months after initiation or modification of therapy.
- Virological blips accepted only if a single viral load measurement has been between 50-200 cop/ml followed by VL  $< 50$  cop/ml without the need to initiate a change in ART and no blip within 12 month window period prior to screening.
- Documented evidence of at least two HIV VL  $< 50$  cop/ml measurements during the past 12 months prior to inclusion: one within 6 months prior to screening.
- HIV VL  $< 50$  cop/ml at screening.
- $BMI > 25 \text{ kg/m}^2$  and one metabolic syndrome condition, which are
  - $BP \geq 130/\geq 85 \text{ mmHg}$  or hypertension medication currently in use or
  - fasting glucose  $\geq 5.6 \text{ mmol/l}$  or  $B\text{-HbA1C} > 42 \text{ mmol/mol}$  or diabetes medication currently in use or
  - $HDL < 1.0 \text{ mmol/l}$  in men and  $< 1.3 \text{ mmol/l}$  in women or triglycerides  $\geq 1.7 \text{ mmol/l}$  or a cholesterol-lowering regimen currently in use or
  - waist circumference  $> 94 \text{ cm}$  in men and  $> 80 \text{ cm}$  in women (or respective cut off values for non-European ethnic groups as defined by International Diabetes Federation).

OR

- ultrasound or biopsy proven hepatosteatosis.

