## 6. Data analysis

The data will be analyzed by the investigators and the study group.

All variables of the data will be analyzed after the last subject's last visit, when the data have been declared complete.

The data will be analyzed using IBM SPSS Statistics v. 22. The differences between the groups will be analyzed by using chi-square, Fisher's exact, Mann-Whitney U test and others, as appropriate.

As there are no earlier ART-switch studies using H-Magnetic resonance spectroscopy for the quantification of liver fat, the calculation of the study power is an estimate. In the STERAL study evaluating the effect of switching from efavirenz (EFV) to RAL vs. continuing Efv-based ART, a statistically significant difference in the liver fat content using CAP (controlled attenuated parameter) was shown with a study sample of 19 +18 subjects after 48 weeks (7,3% decrease in the RAL vs. 11,0% increase in the Efv arm, p = 0,019) (11).

The power of this study is calculated with the assumption of liver fat being 4.4-5.0% in this study group at baseline. This estimation is based on our previous results published in 2002, when the median liver fat was 8% with lipodystrophic patients and 3% with non-lipodystrophic patients (17). Hadigan et al reported liver fat content being >5% in 42% of HIV positive subjects (18). As the liver fat content correlates with visceral fat mass, studying overweight or obese patients with at least one metabolic syndrome component includes patients at high risk for elevated liver fat content.

In the power calculation, we have used a coefficient of variation (CV) of H-Magnetic resonance spectroscopy being 11% (17). To detect a 9% difference between study arms with 80% power, a minimum sample size of 25 + 25 subjects with a 10% drop-out rate is needed.

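### Randomisation is stratified by age, sex and prior regimen, but section 6 uses none of these factors and plans no estimate by prior regimen; the likely cost is power, not false positives

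*Combined protocol and SAP*

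**What the plan says.** Four parts of the protocol bear on this.

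- **Design (section 3).** Two arms, allocated 1:1: "Study subjects will be randomized 1:1 to continue current ART regimens or to switch their PI or efavirenz to once daily raltegravir". Then: "The randomization will be stratified by age, sex and antiretroviral regimens (PI or efavirenz" (the bracket closes there). The total is given in the same section: "The total number of study subjects included in the study is 45".
- **Eligibility (inclusion criteria).** "Current ART includes either a protease inhibitor or efavirenz". No quota or expected share of either class appears anywhere.
- **Aim (section 1) and objectives (section 2).** The hypothesis compares subjects "continuing their current ART regimens (which include a PI or efavirenz) or switching to raltegravir based ART". The section closes with a wider aim, to characterise "the metabolic effects of protease inhibitors, efavirenz and raltegravir in HIV-infected overweight or obese patients". The primary objective is "Baseline to 24-week Change in Liver Fat (measured by proton magnetic resonance spectroscopy", and no objective is split by prior regimen.
- **Analysis (section 6).** "The differences between the groups will be analyzed by using chi-square, Fisher's exact, Mann-Whitney U test", and the sentence ends by allowing other methods where suitable. No stratified or covariate-adjusted analysis, regimen subgroup, interaction or confidence interval is specified.

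**The concern.** Stratifying on prior regimen only makes sense if regimen is thought to matter for outcome. Once the arms are balanced on such a factor, a test that ignores it leaves the variation between PI and efavirenz users in the error term, although that variation no longer contributes to the difference between arms. The standard error is then too large and power is lost, which matters with 45 subjects.

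The wider aim in section 1 also has no analysis attached. Nothing in section 6 would show whether leaving a PI and leaving efavirenz behave alike.

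The trial is open-label and the investigators analyse the data. Leaving adjustment and subgrouping to be settled as suitable means the choice could be made after the results are visible.

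**Working it through.** **1. The plan's own figure.** Inputs from section 6: 9% difference, CV 11%, 80% power, 10% drop-out, 25 + 25 subjects. Alpha is not stated; I assume 0.05 two-sided.

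- Raw scale: n per arm = 2 × (1.960 + 0.842)² × (11/9)² = 23.4, so 24 (25 with the t distribution), before drop-out. With drop-out, 24/0.9 = 26.7, so 27.
- Log scale: n per arm = 2 × (1.960 + 0.842)² × ln(1 + 0.11²) / [ln 0.91]² = 21.2, so 22. With drop-out, 22/0.9 = 24.4, so 25.

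The stated 25 + 25 is reproduced on the log scale. Either way it is a simple two-arm calculation with no term for regimen.

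**2. Assumptions for the effect of ignoring regimen.** 22 per arm (about half of 45, before drop-out), SD of change 11 within each regimen group, a 50:50 PI/efavirenz mix balanced across arms, normal data, the same treatment effect in both groups. The gap is the difference in mean change between PI and efavirenz users. The documents do not give it, so I vary it. The SD of 11 is also an assumption: section 6 gives 11% as the CV of the spectroscopy, not as the between-subject SD of 24-week change.

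**3. Standard error.**

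- Adjusted for regimen: 11 × √(2/22) = 3.32.
- Ignoring regimen: √(11² + gap²/4) × √(2/22).
- Ratio: √(1 + (gap/SD)²/4). Only the ratio of gap to SD matters, so the relative loss does not depend on 11 being right.

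| Gap (points) | Gap/SD | SE ignoring regimen | Excess over adjusted |
|---|---|---|---|
| 0 | 0 | 3.32 | 0% |
| 5.5 | 0.5 | 3.42 | 3% |
| 11 | 1.0 | 3.71 | 12% |
| 16.5 | 1.5 | 4.15 | 25% |

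**4. Error rate and power for a 9-point difference** (simulation, 20,000 runs per setting; a repeat with 40,000 runs agreed to within about half a percentage point).

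| Gap | Mann-Whitney type I | Mann-Whitney power | Adjusted linear model power | van Elteren power |
|---|---|---|---|---|
| 0 | 4.9% | 73% | 76% | 72% |
| 5.5 | 4.5% | 71% | 75% | 71% |
| 11 | 3.0% | 64% | 75% | 71% |
| 16.5 | 1.3% | 52% | 76% | 72% |

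The adjusted model's type I error is about 5% throughout. At zero gap, the 2 to 3 points between Mann-Whitney and the linear model come from using ranks on normal data, not from the stratification.

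**5. Cost of adding age and sex.** Residual degrees of freedom fall from 42 (treatment only) to 39 (treatment, regimen, age, sex). Power for 9 points at SD 11 goes from 75.5% to 75.4%, even if age and sex explain nothing.

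**6. What by-regimen estimates can deliver.** With 45 subjects and a 50:50 mix, there are 11.25 per arm in each stratum.

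- Within-stratum SE = 11 × √(2/11.25) = 4.64. Power for 9 points is 49% (normal) or 46% (t).
- Interaction SE = 4.64 × √2 = 6.56. Power for a 9-point difference between the two effects is 28%; 80% power needs 2.80 × 6.56 = 18.4 points.

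**7. When the mix matters.** If both switches give 9 points, the pooled effect is 9 at any mix. If, as an assumption, leaving a PI gives 4.5 and leaving efavirenz gives 13.5, the pooled effect is 11.7, 9.0 or 6.3 points at 20%, 50% or 80% PI users. At 22.5 per arm, power is 95%, 78% or 48%.

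**The case against.** The strongest reply is that the plan answers the question it asks. The hypothesis in section 1 deliberately pools PI and efavirenz users, no objective in section 2 is split by regimen, and section 6 powers a difference between two arms. Stratifying randomisation balances the arms and does not by itself commit anyone to class-specific estimates. This stands. A reader might infer from section 1 that the trial must estimate PI and efavirenz effects as distinct results, or that pooling is an error. The text lists the drugs but does not say that, and its wording is that of a closing, exploratory aim.

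Second, the open-ended wording of section 6 does not rule out an adjusted model. This also stands: the plan is silent on adjustment rather than committed against it. Nor does it plan intervals that could be called wrong, since it specifies none.

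Third, dependence on the mix arises only if the two switch effects differ, which the documents do not quantify, and a regimen covariate does not remove it; only the stratum estimates show it. This stands too. A reader might use the cited efavirenz-switch study (7.3% decrease against 11.0% increase) to work out what share of efavirenz users the trial needs. That does not carry over: it is CAP at 48 weeks in HIV/HCV co-infected patients, whereas this trial uses spectroscopy at 24 weeks and excludes chronic hepatitis C.

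The reply does not reach the main point. Three factors are built into the randomisation, none is used in the named analysis, and using them costs almost nothing.

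**Conclusion.** The point holds as a choice of analysis that should be improved and fixed in advance. Where regimen predicts change in liver fat, the named rank test gives up power: about 64% against 75% for a 9-point difference if the gap between PI and efavirenz users equals one SD, and about 71% against 75% if it is half an SD. If the gap is zero, adjustment gains and loses almost nothing.

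These figures rest on 22 per arm, SD 11, a 50:50 mix and normal data. The documents supply neither the gap nor the SD of change. With drop-out, or a larger SD, power is lower under every method, but the ordering does not change.

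A reader might infer that the planned test is invalid or raises the risk of a false positive. It does neither; its error rate is at or below the nominal level.

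The missing by-regimen estimate is a smaller matter. It is needed to serve the wider aim in section 1 and to show whether the pooled result hides a difference, but at this size it can only be descriptive.

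**What to change.** In section 6:

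1. Keep the pooled two-arm comparison as primary. Analyse 24-week change in liver fat with a linear model containing treatment, prior regimen (PI or efavirenz), age and sex, and report the treatment difference with a 95% CI. If a rank method is preferred, use a van Elteren test stratified by regimen in place of Mann-Whitney U.
2. Report the treatment difference with a 95% CI within the PI and efavirenz strata, together with the treatment-by-regimen interaction estimate and its 95% CI. Label these descriptive and unpowered. Do not size the trial for them.
3. Report the number of PI and efavirenz users in each arm, so that the pooled result can be read against the mix enrolled.

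The cost is a rewritten paragraph and a decision on the primary method, made before any outcome data are examined. No subjects, visits or measurements are added. The model uses three more degrees of freedom than an unadjusted comparison. The within-regimen intervals will be wide and the interaction has little power, so the text should say that a non-significant interaction is not evidence of equal effects.
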